1.2 Randomisation

All houses in five urban study area districts (Bandim-I, Bandim-II, Cuntum-I, Cuntum-II and Belem) were randomised to intervention or control group stratified by zone (Bandim-I: zones 1-9, Bandim-II: zones 1-8, Cuntum-I: zones 1-9, Cuntum-II: zones 2-4, and Belem zones A-E).

1.3 Baseline Interview

Prior to enrolment a list of potentially eligible people was extracted from the HDSS databases. At the enrolment visit, information on sex and age was confirmed, and all participants were interviewed on chronic diseases, symptoms on the day of enrolment, medicine intake in the past month and admissions within the past 3 months. We aimed to have minimal physical contact. Therefore, weight was assessed using a visual scoring system, based on the field assistant's perception of the participant's bodily appearance, scoring weight from 1-10¹. The presence of a BCG and/or smallpox vaccination scar was also assessed by visual examination.

1.4 Follow-up

Participants were followed up through telephone calls and registration of consultations at two health centres in the study area where they could seek consultations free of charge. Furthermore, all individuals are also followed through the HDSS of Bandim Health Project.

1.4.1 Telephone follow-up

We called all study participants every 4 weeks between enrolment and 6 months of follow-up to collect information on health outcomes. In some cases, information was provided by a relative in the same household. For all trial participants, we asked whether they, since enrolment (for the 1st telephone interview call) or since the last call, had experienced any of the following symptoms:

Common cold, Cough, Fever, Breath-lessness, Vomiting, Diarrhoea, Loss of sense of smell, Loss of sense of taste, Headache, Sore throat, Body aches, Extreme tiredness, Other symptoms (If yes: which?)

For "yes" to either of these symptoms, further questions on timing were asked (today, within the last week, 1-<2 weeks ago, 2-<3 weeks ago, 3 or more weeks ago)

Information was also collected on:

Use of other medicine than habitual, COVID-test performed (and result thereof), Weight loss during the interval

Finally, all participants were asked if they had sought consultation or been admitted to hospital during the interval. If yes, they were asked when, where, reason for consultation/admission and whether they had received a diagnosis.

1.4.2 Passive case detection

All participants were informed that they could seek consultation free of charge at two health centres in the study area. Following a consultation at the health centre, information on date of consultation, symptoms, diagnostic tests, and prescribed treatment were collected from the health centres consultation books.

1.5 Outcomes

All outcomes are assessed within the follow-up period of 6 months.

1.5.1. Primary outcome

The primary outcome is a composite outcome of the first of death, hospitalisation for infection and/or a recorded consultation for infection at the health centre. Thus, the information can come from either the telephone follow-up, the health centre data or the HDSS.

1.5.2. Secondary outcomes

The secondary outcomes are other measures of infectious disease morbidity (prespecified: a and b, specified after trial initiation: f) and the three separate components of the composite outcome (c, d, and e).

a) Episodes with self-reported infectious disease morbidity: Through the telephone follow-up any reported episode which includes Common cold, Cough, Fever, Breath-lessness, Vomiting, Diarrhoea, Sore throat, or Body aches will be counted as an infectious disease episode. Following an infection, the person will re-enter the at-risk-population 2 weeks later.

b) Episodes with self-reported infectious disease morbidity suspected to be caused by COVID-19: Through the telephone follow-up any reported episode which includes three or more of the following: fever, cough, sore thought, extreme fatigue, or loss of smell/loss of taste). Following an infection, the person will re-enter the at-risk-population 2 weeks later.

c) Mortality: All-cause mortality: Death due to any cause during the follow-up period. If there are cases of inconsistency between different sources of information, the HDSS information will be considered superior.

d) Hospital admission: Hospital admission for infectious disease. Self-reported admission with symptoms or diagnosis classified as caused by infection. Analysed as a repeated event. Following an admission, the person will re-enter the at-risk-population 2 weeks later.

e) Consultations for infectious disease: Consultation for infectious disease registered at one of the two health centres. Analysed as a repeated event. Following a consultation, the person will re-enter the at-risk-population 2 weeks later.

f) Reported consultations: Any consultation for infectious disease reported to have occurred at any health facility.

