## **OBJECTIVES**

To test if OPV can reduce the risk of COVID-19 among adults aged 50 years and above in an urban African setting.

Primary outcome: Mortality and severe morbidity (hospitalisation or consultations for infections) during 6 months of follow-up.

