#### **Outcomes:**

**Primary outcome:** Composite outcome of the first of death, hospitalisation for infection and/or consultation for infection at the health centre

**Secondary outcomes:** Episodes with self-reported infectious disease morbidity. Episodes with self-reported infectious disease morbidity suspected to be caused by COVID (three or more of the following: fever, cough, sore throat, extreme fatigue, loss of smell/taste). Either of the components of the composite outcome described above included repeated events.

**Statistical analysis:** Data will be analysed in Cox proportional hazards models, with time since randomization as the underlying time, to provide hazard ratios (HRs) with 95% CIs for comparison of the intervention and control groups. With the exception of the primary outcome, data will be analysed as a multiple failure time data set. Age in groups of 5 years and suburb will be adjusted for. Clustering within houses will be adjusted for.

**Sample size:** The Bandim Health Project has purchased 1700 doses of OPV. The trial will include participants until the 1700 doses have been used. With a samples size of 3400, half getting OPV, the trial can show a reduction in the combined risk of mortality (which has been around 2% in this age group in our study area) and severe morbidity after 6 months of follow-up from a total of 10% to 7.2% (i.e. a 28%

reduction) with 80% power and alpha of 0.05. Since only individuals above the age of 50 years are eligible to enter the trial, only few houses will have several participants and we expect a very limited effect of clustering.

**Explanation to participants:** Participants will be given thorough information about Coronavirus, about precautions to be taken, and about the study (Appendix 2).

**Timeline:** A Gantt diagram is presented in Figure 1.

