1.6.2 Multiple testing

P-values will not be corrected for multiple testing. The secondary outcomes are testing the robustness of the findings, by examining if the pattern is similar 1) when milder illness is included, 2) with narrower COVID-19 symptom classifications, and 3) for the separate components of the composite outcome. Consequently, $p \leq 0.05$ will not be employed as a threshold for statistical significance for secondary outcomes.

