2.3 Analyses of secondary outcomes

For our secondary outcomes a) episodes with self-reported infectious disease morbidity reported through the monthly follow-up calls, b) episodes with self-reported infectious disease morbidity suspected to be caused by COVID-19 (three or more of the following: fever, cough, sore throat, extreme fatigue, loss of smell and/or taste) and f) reported consultation for infectious disease, we will analyse repeated events data sets including all individuals for whom information was obtained through the telephone follow-up.

For the separated components of the composite outcome the population depends on the outcome assessed: c) mortality is for all individuals, d) hospital admissions for all individuals for whom a telephone follow-up was conducted and e) recorded consultation for all individuals alive in the study area.

The analyses of the secondary outcomes are described in more detail in table 2, 3 and 4.

¹If we identify evidence for non-proportionality, we will still report the marginal hazard ratios, but supplement this estimate by hazard ratios for 2-3 properly selected categorical time-periods identified based on the aforementioned proportionality investigations.

² If there is indication of non-proportionality based on assessment of the log-log curves, we will test for non-proportionality by replacing the term `tezp(_t)` with `tezp(_t>s)` for specific values of `s`.

Table 2: Analyses of secondary outcomes (a, b, d, f) – reported morbidity outcomes

Population	Per-protocol population
Observation period	From: enrolment To: 183 days after enrolment Censoring: Death, Date of loss to follow-up (last telephone interview)
Failure definition	
 a) Self-reported infectious disease morbidity. b) Self-reported infectious disease morbidity suspected to be caused by COVID-19 d) Hospital admission for infectious disease f) Reported consultation for infectious disease 
Repeated events. Episodes within 2 weeks of each other will be considered as related to the same infection. Thus, a trial participant will re-enter the population-at-risk 14 days after the episode start, provided that there has been a period without reported symptoms in the meantime.

Statistical tools	Repeated Cox-proportional hazards model, adjusted for the zone (stratification variable in the randomisation), age and box1 factors. Robust standard error to adjust for same-house clustering.

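### Secondary outcome a leaves out loss of smell and taste, so some mild episodes of the kind the trial targets count in neither a nor b; adding the two symptoms is a small, nearly free improvement

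*SAP*

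**What the plan says.** The Protocol (Outcomes) names the outcome only as "Episodes with self-reported infectious disease morbidity" and gives no symptom list. The operative definition is in SAP 1.5.2 a): "any reported episode which includes Common cold, Cough, Fever, Breath-lessness, Vomiting, Diarrhoea, Sore throat, or Body aches will be counted as an infectious disease episode". Any one of the eight symptoms is enough.

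SAP 1.4.1 shows that each call asks about twelve named symptoms plus a free-text category. The run "Loss of sense of smell, Loss of sense of taste, Headache, Sore throat, Body aches, Extreme tiredness, Other symptoms" includes the four named symptoms that are asked but not used in a: loss of smell, loss of taste, headache and extreme tiredness.

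Outcome b, suspected COVID-19, requires "three or more of the following: fever, cough, sore thought, extreme fatigue, or loss of smell/loss of taste". SAP 2.3 restates the items as "fever, cough, sore throat, extreme fatigue, loss of smell and/or taste". Both versions, like the Protocol, write smell and taste as one item.

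SAP 1.6.2 treats the secondary outcomes as robustness checks. One of them asks whether the pattern is similar "when milder illness is included", which is the role that a fills. The Protocol's objective is "To test if OPV can reduce the risk of COVID-19 among adults aged 50 years and above".

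**The concern.** Outcome a is the broad measure and b the narrower one. One would expect the broad measure to recognise every symptom that the SAP treats as a marker of suspected COVID-19 and that could be the main complaint in a mild case. It does not do so for smell and taste loss, although the data are collected at every call. In a trial whose objective is COVID-19, the outcome meant to bring in milder illness then drops some mild illness of the targeted kind.

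A second question arises from the same list. Body aches or breathlessness alone count as an infection. In adults over 50 either may have a non-infectious cause, and OPV would not be expected to change such episodes.

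**Working it through.** The plan gives no expected rate, effect or power for outcome a, so there is no figure of its own to reproduce. The check applies the written rules to the symptom list.

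**Inputs**
- Twelve named symptoms (SAP 1.4.1); the free-text category is left aside.
- Rule a: at least one of eight (SAP 1.5.2 a).
- Rule b: at least three of five, with smell/taste as one item (SAP 1.5.2 b and 2.3). Extreme fatigue in b is taken to be the call item on extreme tiredness.

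**Step 1: combinations that fail a.** Non-empty combinations of twelve symptoms: 2^12 − 1 = 4095. Those that fail a use only the four unlisted symptoms: 2^4 − 1 = 15. The other 4095 − 15 = 4080 count.

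**Step 2: how many of the 15 contain smell or taste loss.** Those without it use only headache and tiredness: 2^2 − 1 = 3. The rest: 15 − 3 = 12.

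**Step 3: does b recover the 12?** Of b's five items, only tiredness and smell/taste can be present in these combinations, so the highest score is 2 and three are needed. None of the 12 counts in b. If smell and taste were instead scored as two items, smell + taste + tiredness, with or without headache, would reach 3. Those two combinations would then meet b while failing a.

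**Step 4: do other outcomes recover them?** Outcome d (admission for infection) and outcome f (reported consultation for infection at any facility) do not use this list. They could include such a person if care was sought and the cause was classed as infection. SAP 2.6.1 narrows the planned outcomes and does not widen a.

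**Step 5: effect on the estimate.** Let m be the share of infectious episodes missed. If m is the same in both arms, the hazard ratio is unchanged in expectation. The standard error of its logarithm rises by a factor of about 1/√(1 − m), roughly m/2 in relative terms when m is small. The documents give no value for m.

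**Step 6: isolated aches or breathlessness.** Let q be the share of counted control-arm episodes that are non-infectious, with a hazard ratio of 1, and let HR be the true ratio for infections. The observed ratio is then about HR × (1 − q) + q, which lies nearer 1. Purely to show the shape, put in 0.72, the Protocol's 7.2%/10% for the primary composite:

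| Assumed q | Observed ratio |
|---|---|
| 10% | 0.72 × 0.9 + 0.1 = 0.748 |
| 20% | 0.72 × 0.8 + 0.2 = 0.776 |
| 30% | 0.72 × 0.7 + 0.3 = 0.804 |
| 40% | 0.72 × 0.6 + 0.4 = 0.832 |

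Neither input is given for outcome a, so these are not estimates for this trial.

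**The case against.** The case for leaving the list alone has real weight.

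- Use in b does not show that a symptom suffices by itself. B requires three items, and it also contains extreme fatigue, whose absence from a is easy to accept. This stands: the documents do not contradict themselves, and adding smell and taste rests partly on clinical judgement.
- Twelve combinations are not twelve episodes. An episode is missed only when smell or taste loss comes with none of eight common symptoms. This stands and limits the gain.
- Outcome a is broad by design, and every symptom proxy takes in some non-infectious illness. Isolated cough, vomiting or diarrhoea would also qualify. SAP 1.6.2 sets no significance threshold for secondary outcomes, and the symptom-free condition for re-entry (SAP Table 2) limits repeat counting of persistent complaints. The primary outcome does not use the list. Whether long-standing pain would be recorded as body aches depends on the follow-up questionnaire (Protocol Appendix 6), which is not among the documents. Together these points rule out replacing the main definition with a stricter one.

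Three stronger readings are tempting. A reader might infer that the missed episodes enter no self-reported outcome at all; that holds only for a and b, since d or f may include them. A reader might infer that the omission biases the hazard ratio; under equal missing in both arms it does not. A reader might take the dilution figures as the expected attenuation; they join an assumed q to an effect borrowed from a different outcome.

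The objection does not answer why a symptom collected at every call and used for suspected COVID-19 is absent from the broad infection measure. The SAP gives no reason.

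**Conclusion.** The point holds as a minor improvement. As written, outcome a does not count an episode of smell and/or taste loss that comes alone or with only headache and/or extreme tiredness, and b does not count it either. This follows from the rules and needs no assumption beyond reading smell/taste as one item in b, as the documents write it.

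The number of such episodes cannot be derived from the documents and is probably small. The main cost is lost events. That no bias arises assumes similar missing in the two arms. Controls receive advice only and the outcome is self-reported, so this is not assured, but nothing in the documents points to a difference.

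That isolated body aches or breathlessness could pull the hazard ratio for a towards 1 is plausible but is clinical inference, and its size cannot be estimated here. It supports an added sensitivity analysis and no more.

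**What to change.** In SAP 1.5.2 a), add loss of sense of smell and loss of sense of taste to the qualifying list before analysis. Only three combinations of the named symptoms would then fail a (headache, tiredness, or both), and every episode that meets b would meet a, whichever way smell and taste are scored. If outcome data by arm have already been seen, keep the present list as the main definition and report the wider one as a labelled sensitivity analysis. The SAP describes follow-up in the past tense, so the timing should be stated.

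Optionally, keep the any-one rule as the main definition and add a sensitivity analysis that does not count episodes consisting only of body aches and/or breathlessness. State whether accompanying headache or tiredness changes that classification.

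The cost is a wording change and a recode of answers already collected. The Protocol has no symptom list to amend. The addition may bring in an occasional non-infectious smell or taste complaint. The optional analysis would leave out some true infections that present only with aches or breathlessness, which is why it should stand beside the main definition and not replace it.

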1.6 Statistical analyses

1.6.1 Statistical model

The outcome rates will be compared by randomisation arm in Cox proportional hazards models, with time since randomization as the underlying time, to provide hazard ratios (HRs) with 95% CIs. The main results will be adjusted for age (in 5-year age-bands) and zone (based on which the randomisation was stratified). Clustering within houses will be adjusted for. With the exception of the primary outcome, data will be analysed as a multiple failure time data set. All statistical tests will be 2-tailed and $p \leq 0.05$ considered statistically significant.

Prior to implementing the trial, stories of experimental COVID-19 vaccines planned to be tested in Africa had been circulating on social media, and many perceived the OPV, which we were providing in the present trial, as one of these experimental vaccines. We have therefore encountered high refusal rates, especially in the intervention arm. As this may have resulted in baseline imbalances, we will present both the 'crude' result (only adjusted for age and zone) and adjusted results where we will adjust for background factors which affect the estimated effect of OPV on the primary outcome by more than 10%. The background factors to be investigated are presented in Box 1.

In subsequent analyses of the trial dataset, we intend to use targeted maximum likelihood estimation (TMLE) (section 2.6.2). These analyses will be reported later.

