2.1 Baseline comparison

Descriptive statistics: We will describe participant flow by group allocation in a flowchart. For participants included in the main analysis, we will describe background factors. Background factors will be summarised by counts (percentages), means (standard deviation) or medians (interquartile range) as appropriate. Information on the proportion with missing information will be provided.

Box 1: Background factors which will be presented by intervention and control group

Suburb (group of zones)* Age* Sex Formal education (highest completed grade) Whether signed or fingerprinted the consent form Visual classification of weight Prior chronic illness (major types: Hypertension/Diabetes) Medicine intake in the month prior to enrolment Admissions during the past 3 months
--

*All effect estimates will be presented adjusted for age and zone. For the other listed variables, they will be included as co-variates if adjusting for them changes the effect estimate by at least 10%

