2.2 Primary analysis of primary outcome

The rates of the primary outcome (a composite outcome of the first of death, hospitalisation for infection and/or consultation for infection at the health centre) within 6 months after enrolment will be compared in Cox proportional hazards models with time since enrolment as the underlying timescale.

The primary analysis of the primary outcome is described in more detail in table 1.

Table 1: Primary analysis of primary outcome

Population	Per-protocol population
Observation period	From: enrolment To: 183 days after enrolment Censoring: None
Failure definition	Death or first post-enrolment admission for infection and/or consultation for infection registered at a health centre.
Statistical tools	Cox-proportional hazards model, adjusted for the zone (stratification variable in the randomisation) and age. Robust standard error to adjust for same-house clustering.
Outline stata code	<pre>stset outdate, f(combinedoutcome=1) origin(dateenrol) enter(dateenrol) exit(dateenrol+183) stcox group b11.zone b50.agegroup b1.box1var1 b1.box1var2 ..., vce(cl house) Where [box1var1] [box1var2] etc. are the background factors from Box1 which affect the [group]-estimate by at least 10% Check of proportional hazards assumption¹: estat phtest, detail stphplot, adj(zone agegroup box1var box2var) strata(group)² stcox group, strata(zone agegroup box1var box2var) vce(cl house) /// tvc(group) tezp(_t)</pre>

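### SAP text and code disagree on which model gives the primary p-value, and the 10% rule for the adjusted model is under-specified and can miss joint confounding

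*SAP*

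**What the plan says.** SAP 1.6.1 states: "The main results will be adjusted for age (in 5-year age-bands) and zone". It then reports high refusal, especially in the intervention arm, and says that two results will be shown: a 'crude' one with age and zone only, and "adjusted results where we will adjust for background factors which affect the estimated effect of OPV on the primary outcome by more than 10" per cent. The Box 1 footnote in SAP 2.1 says of the other listed variables that "they will be included as co-variates if adjusting for them changes the effect estimate by at least 10" per cent. Seven factors are subject to this screen: sex, education, signed or fingerprinted consent, visual weight, chronic illness, recent medicine intake and recent admissions.

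Table 1 in SAP 2.2 is the specification of the primary analysis. Its 'Statistical tools' row lists zone and age. Its code reads "stcox group b11.zone b50.agegroup b1.box1var1 b1.box1var2 ..., vce(cl house", and a note defines the extra terms as the Box 1 factors that pass the screen. SAP 1.1 puts all analyses on the per-protocol population. SAP 2.6.2 plans a TMLE re-analysis because of the differential refusal; 1.6.1 says it will be reported later.

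**The concern.** There are two linked problems.

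First, the specification of the primary analysis contradicts itself on the covariates, so it is unclear which estimate is tested at the 5% level if the two results differ.

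Second, the screen suits its purpose poorly. Refusal that differs by arm can shift several characteristics together, and randomisation of houses does not protect the people who actually enrol. If each factor is judged alone, several moderate shifts in the same direction can all fall below 10% and stay out of the model, although their product is large. Choosing covariates by their effect on the OPV estimate also makes the model depend on the result, and the planned confidence interval does not reflect that choice. The set chosen on the primary outcome is then carried into Tables 2-6.

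**Working it through.** **1. The passages side by side**

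| Place | Covariates or threshold |
|---|---|
| SAP 1.6.1, main results | age, zone |
| Table 1, 'Statistical tools' | zone, age |
| Table 1, code | zone, age, selected Box 1 factors |
| Tables 2-6, 'Statistical tools' | zone, age, Box 1 factors |
| Threshold in 1.6.1 and Tables 2, 4, 5, 6 | more than 10% |
| Threshold in Box 1 footnote and Tables 1, 3 | at least 10% |

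No passage gives the scale (HR or log-HR), the base model, or whether factors are tried singly, in sequence or together.

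**2. The plan's own figure**

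The Protocol's sample size paragraph says "With a samples size of 3400, half getting OPV, the trial can show a reduction" "from a total of 10% to 7.2% (i.e. a 28" per cent reduction) "with 80% power and alpha of 0.05". Expected events are 1700 × (0.10 + 0.072) = 292.4. By Schoenfeld's formula with HR 0.72, √(292.4/4) × |ln 0.72| − 1.96 = 8.55 × 0.3285 − 1.96 = 0.85, which gives 80.2% power. The stated 80% is reproduced. The number 3400 itself comes from the doses bought: "The trial will include participants until the 1700 doses have been used".

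**3. What one factor needs to pass (HR scale, tested singly)**

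With 30% prevalence in one arm and p in the other, the shift in the OPV estimate is (1 + p(HR − 1)) / (1 + 0.30(HR − 1)). Setting this to 1.10 gives p = 0.53 for a factor with HR 1.5, 0.43 for HR 2 and 0.38 for HR 3. At HR 1.5 and 30% vs 38%, the shift is 1.19/1.15 = 1.035, well below the threshold. Seven independent factors of this kind compound to 1.035^7 ≈ 1.27.

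**4. Bound from compounding**

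Take k factors just under the threshold, all in one direction, with no true effect and 10% risk in both arms (340 events). The test statistic shifts by √(340/4) × ln(bias) = 9.22 × ln(bias).

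| k | Bias in HR | Two-sided rejections |
|---|---|---|
| 1 | 0.90 or 1.10 | 16% or 14% |
| 2 | 0.81 or 1.21 | 49% or 42% |
| 3 | 0.73 or 1.33 | 83% or 75% |

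A bias of 0.73 is about the whole planned effect (0.72).

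**5. Simulation**

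Assumptions not in the documents: true HR 1; 1700 per arm; binary factors with HR 1.5; Poisson regression as a stand-in for Cox; no house clustering; single-factor screen on the HR scale. Unless stated, prevalence is 30% vs 38%. The first row used 10% control risk. The main 30% vs 38% scenario used about 8.5% events. There were 200-400 runs per scenario where recorded; with 300 runs the Monte Carlo standard error is √(0.5 × 0.5/300) = 2.9 points near 50%, and 1.3 points near 5%.

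| Scenario | HR under the rule | False positives |
|---|---|---|
| Seven factors, 30% vs 30% | 1.01 | 4.5% |
| Seven, four one way and three the other | 1.04 | 6% |
| Seven, 30% vs 33% | 1.09 | 9% |
| Seven, latent correlation 0.6 | 1.02 | 7-8% |
| Three factors only | 1.09 | 12-13% |
| Seven, latent correlation 0.3 | 1.23 | 42% |
| Seven, independent | 1.25-1.27 | 47-52% |
| Seven, independent, 34 zones in the model | 1.23 | 42% |

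In the last two scenarios the screen selected no factor. Including all factors gave an HR of 0.99-1.01 and about 3.5-7% false positives, with a standard error 1-3% larger.

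**6. Dependence on the reading**

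For seven independent factors at 30% vs 38%, a joint test of all factors triggers adjustment in every run (HR 1.00, 5% false positives). If the 10% applies to the log-HR, five of the seven are selected on average (HR 1.05, 17%). The log-HR threshold also moves with the estimate. At HR 0.72 it is 0.1 × 0.3285 = 0.033, about a 3% change in HR, and it shrinks towards zero as the estimate nears the null.

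**The case against.** The documents do lean one way on the primary model. SAP 1.6.1 names main results, the 'Statistical tools' row agrees, and the Protocol's analysis paragraph adjusts only for age, suburb and clustering. A reader might infer that nothing in the SAP designates a main estimate; that goes too far. What remains is that the code in the primary-analysis table contradicts the designation. If the designation is followed, the deciding estimate carries none of the adjustment that the SAP introduces because of refusal.

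The 40-50% figure needs seven independent factors, all imbalanced the same way. Several Box 1 items plausibly overlap (education with signing; chronic illness with medicine and admissions), and strong overlap makes the screen work: at latent correlation 0.6 a factor was selected in 94% of runs. One-at-a-time testing on the HR scale is the natural reading but is not stated. This objection stands, and it limits the size of the problem rather than removing it.

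Box 1 factors are tabulated by arm and both results are shown, so gross imbalance would be visible. TMLE uses a fixed covariate list without the screen, but it comes later and omits education, past admissions and zone. Reusing one covariate set for the secondary outcomes avoids outcome-by-outcome selection, and SAP 1.6.2 sets no significance threshold for them, so that part carries little weight.

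Full adjustment is not free either: SAP 1.2 lists 9 + 8 + 9 + 3 + 5 = 34 zones, hence 33 zone terms before any Box 1 factor.

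**Conclusion.** The inconsistency in Table 1 stands on the text alone, as does the under-specification of a rule driven by the treatment estimate. On the one-at-a-time, HR-scale reading, the rule can also leave material joint confounding in the adjusted estimate. With no true effect, false positives range from about 5%, through about 8% and 12-13%, to about 40-50%, depending on how many factors are imbalanced, in which direction, and how correlated they are.

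Two stronger conclusions are tempting but unsupported. One is that about half of null trials would be declared positive; that is near the worst case. The other is that the adjusted result will often equal the crude one; the documents give no baseline data from which to judge that. With no imbalance the screen does no harm. The case for change rests on the contradiction, the imbalance that the SAP itself expects, and the small cost of a fixed covariate set.

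**What to change.** Before outcome data are analysed by arm:

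- Delete the 10% screen in SAP 1.6.1, Box 1 and Tables 1-6.
- Prespecify one covariate set: age, zone and all seven other Box 1 factors. Code visual weight and education in few categories or as linear terms, and state how missing Box 1 values are handled. If the number of parameters is a concern, use zone as strata.
- Name that model as primary, make Table 1's text and code agree, and report the age-and-zone model beside it as supportive.

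The cost is SAP wording plus about 10 parameters. With 33 zone terms that is 43, or 292/43 ≈ 6.8 events per parameter before the age bands are counted; this is the reason for sparse coding or stratification. The standard error rose by 1-3% in simulation. The change gives no protection against selection on unmeasured characteristics.
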